Observation period: The observation period (duration of treatment with Anoro Ellipta) in each patient will be 1 year after the initiation of prescription of the product.

Planned registration period: February 2015 to January 2017

When the number of registered patients reaches the planned sample size, however, the registration may be discontinued before completion of the above-mentioned registration period.

7. Study Method

This investigation will be conducted by the central registration system. In the investigation, the electronic data capture (EDC) system will be used for case registration and data collection.

- 1) Request for the investigation and contract
 - (1) The medical representative (MR) will explain the study objectives, study population, study items, study method, etc. to the potential investigators, etc. of the medical institutions where Anoro Ellipta has been adopted and where the product is delivered, and request them to cooperate with the investigation.
 - (2) Once agreement on cooperation with the investigation is obtained, a written contract should be concluded with the head (e.g., the director) of the medical institution prior to initiation of the investigation, and then the registration should be started.

Issuance of user ID and password
 After conclusion of the contract, the ID and password necessary to log in the EDC system will be issued.

- 3) Registration of patients
 - (1) The investigator will enter the information of patients for whom prescription of Anoro Ellipta is initiated after conclusion of the contract and who are listed in "3. Study Population" in the EDC system within 14 days after the initiation of prescription of Anoro Ellipta (the date of the initiation of prescription should be regarded as Day 1) to complete the registration of the patients.
 - (2) When the number of registered patients reaches the contracted sample size, registration of patients at the study site will be stopped.
- 4) Collection of data and entry in the EDC system
 - (1) The investigator will confirm the study items such as the characteristics of the registered patients.
 - (2) The investigator will request the registered patients to fill out the "COPD Assessment Test (CAT)" at the initiation of treatment with Anoro Ellipta, and at 1 month and 1 year after the initiation of treatment (or at the discontinuation/completion of treatment if treatment with Anoro Ellipta is discontinued/completed).

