 - (3) The investigator will retrieve the CAT of the registered patients, check the content, and enter the information in the EDC system.
 - (4) During the observation period, the investigator will review the information regarding the safety and efficacy, etc. If a patient does not visit the study site during the observation period, the investigator will obtain information regarding AEs, etc. by telephone, etc. as far as possible.
 - (5) The investigator will enter the information of the registered patients obtained at 1 month and 1 year after the initiation of treatment with Anoro Ellipta (or at the discontinuation/completion of treatment if treatment with Anoro Ellipta is discontinued/completed), and send it.

8. Study Items

The investigator will collect information regarding the following items, etc. as far as possible and enter it in the EDC system.

- Information regarding the medical institution
 Name of the institution, department, and investigator
- 2) Patient characteristics (at the initiation of prescription of Anoro Ellipta) Identification number, sex, age or year of birth, date of the initiation of prescription of Anoro Ellipta, hospitalization status, height, body weight, reason for use of Anoro Ellipta, type of COPD, stage classification, duration of COPD, history of cigarette smoking, Brinkman index, and presence or absence

of complications (bronchial asthma, cardiovascular disorder, renal impairment, hepatic impairment other than the primary disease, etc.) and their names To protect the confidentiality of the identification of individual patients, the identification number will be a unique number assigned to each patient by the investigator, etc. In this investigation, any other diseases or symptoms than COPD that have existed prior to the initiation of treatment with Anoro Ellipta will be handled as "complications".

- 3) Prior medication for COPD (4 weeks before the initiation of treatment)

 Presence or absence of prior medication for COPD 4 weeks before the initiation of treatment, and the category and product name of the medication
- 4) Status of treatment with Anoro Ellipta
 Unit dose and daily dosing frequency of Anoro Ellipta, start and end dates of
 treatment, and reason for dosage modification during the observation period
- 5) Concomitant medications Presence or absence of concomitant medications during the observation period, and the names and reasons for use of these medications

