- 6) Concomitant therapies for COPD (other than medications)

 Presence or absence of concomitant therapies for COPD during the observation period, and the name of the therapy
- 7) COPD exacerbations

 Number of COPD exacerbations during t

Number of COPD exacerbations during the 1-year period before and after the initiation of treatment with Anoro Ellipta

8) Bronchial asthma-related intubation and death

Presence or absence of intubation due to an exacerbation of bronchial asthma and the presence or absence of bronchial asthma-related death during the observation period

Patients with COPD often concurrently have asthma, and "bronchial asthmarelated intubation and death" are set as Safety Considerations in this investigation, and information regarding exacerbations of bronchial asthma during the observation period will be collected as AEs.

9) Respiratory function test (spirometry)

Presence or absence of use of short-acting beta₂-agonists, forced expiratory volume in one second (FEV₁), and forced vital capacity (FVC) at the initiation of treatment with Anoro Ellipta, at 1 month and 1 year after the initiation of treatment, on the day of assessment at the time of discontinuation/completion, and within 4 hours before measurement.

10) COPD assessment test (CAT)

Information in the "COPD Assessment Test (CAT)" filled out by patients at the initiation of treatment with Anoro Ellipta, at 1 month and 1 year after the initiation of treatment, and at the time of discontinuation/completion.

11) Global efficacy assessment

One year after the initiation of treatment with Anoro Ellipta or at the discontinuation/completion of treatment, the efficacy of the product will be assessed comprehensively on a scale of two categories, "effective" or "not effective", based on the progress of subjective symptoms and clinical findings, changes in respiratory function test results, COPD exacerbations, changes in CAT scores, etc., from the initiation of treatment to the completion of the observation period. In case the efficacy cannot be determined for some reason, it will be considered as "indeterminable", and the reason should be entered in the EDC system.

- 12) Status of continuation of treatment with Anoro Ellipta at the completion of the observation period
 Status of the continuation of treatment at 1 year after the initiation of treatment.

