 - [3] Number of patients included in the analysis set for Efficacy 1 (spirometry), number of patients excluded from the analysis set and the reason for exclusion
 - [4] Number of patients included in the analysis set for Efficacy 2 (global efficacy assessment and CAT score), number of patients excluded from the analysis set and the reason for exclusion
 - (2) Patient demographic and baseline characteristics

Distribution of patient demographic and baseline characteristics

- Stage classification, duration of COPD, past treatment history, type of concomitant medications/therapies, history of cigarette smoking, age, body weight, complications, presence or absence of bronchial asthma, etc.
- · CAT scores, number of COPD exacerbations
- Spirometry
- (3) Items related to safety
 - [1] Incidence of ADRs (including infections, hereinafter the same) by MedDRA SOC and PT
 - [2] Priority study item: MedDRA codes should be identified.
 - Cardiovascular events, effects on glucose, effects on potassium, tremor, urinary retention, effects on eyes, gallbladder disorder, intestinal obstruction, anticholinergic effect, lower respiratory tract infection, and pneumonia
 - [3] Explorative assessment of factors (patient demographic and baseline characteristics) that may affect the presence or absence of ADRs and the presence or absence of ADRs set as the priority study item
 - [4] Subgroup analyses (elderly, etc.) by the presence or absence of ADRs and the presence or absence of ADRs set as the priority study item
- (4) Items related to efficacy
 - [1] Efficacy 1
 - · Distribution of FEV1
 - Explorative assessment of the effects of factors (patient demographic and baseline characteristics) that may affect FEV1
 - Subgroup analyses (elderly etc.) by FEV1
 - [2] Efficacy 2
 - · Distribution of global efficacy assessment and CAT score
 - Explorative assessment of the effects of factors (patient demographic and baseline characteristics) that may affect the efficacy and CAT score
- 2) Analysis methods

For re-examination

Protocol No. 200311

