For factors that may affect the items related to the safety and efficacy, etc., the odds ratios and their 95% confidence intervals will be calculated, as appropriate. The results will be graphically presented using a forest plot, etc., as appropriate. For comparison of the scores, etc., the mean values and quartile points, etc. of the values at the measurement time points and the changes from baseline will be calculated and graphically presented using a boxplot, as appropriate.

10. Publication of Study Results

Regarding the results of this investigation, information will be provided, as appropriate, to clinical sites as a final report as presentations at conferences and published articles, etc. taking an appropriate timing and number of collected patients, etc. for "proper use" and to "ensure safety" into consideration.

11. Organization

- 1) Same as the Risk Management Plan
- 2) Person responsible for the investigation: Manager, Planning Group, PMS Department

12. Name and Address of the Contractor, and the Scope of Outsourced Operations

1) Registration operations

Contractor: CMIC Co., Ltd.

Scope of outsourced operations: patient registration, self-inspection, and other related operations

2) Data management operations

Contractor: CMIC Co., Ltd.

Scope of outsourced operations: CRF data entry, follow-up investigation, self-inspection, and other related operations

3) Data tabulation operations

Contractor: CMIC Co., Ltd.

Scope of outsourced operations: data tabulation, data analysis, self-inspection, and other related operations

4) Electronic data capture (EDC) operations

Contractor: FUJITSU FIP CORPORATION

Scope of outsourced operations: EDC system development, self-inspection, and other related operations

13. Progress of the Investigation and Evaluation of the Results Obtained or the Timing of Milestones for Reporting to the PMDA and Their Rationales

- At the time of a periodic safety report: To conduct a comprehensive review of the safety information
- At the time of submission of the application for re-examination: To prepare a final report based on the tabulation/analysis results obtained from fixed data in all retrieved CRFs.

14. Additional Measures That May Be Implemented Based on the Study Results and the Decision Criteria for the Initiation of These Measures

At the milestone time points, the Risk Management Plan, including the following contents, will be reviewed.

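### Concomitant medications and therapies are treated as baseline factors but recorded only as any use during follow-up, so a drug started to treat an ADR can appear as a risk factor for it

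*Protocol*

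**What the plan says.** **Collection.** Section 8 item 5) asks for "Presence or absence of concomitant medications during the observation period, and the names and reasons for use of these medications". Item 6) asks for "Presence or absence of concomitant therapies for COPD during the observation period, and the name of the therapy". Under Section 6 the observation period is the duration of treatment and "will be 1 year after the initiation of prescription of the product". The schedule in Section 17 runs both items through to discontinuation or completion, whereas patient characteristics and prior medication are taken once, at initiation. Neither concomitant item is in the Section 8 item 2) list of characteristics at initiation.

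**Classification.** Section 9 1)(2), on demographic and baseline characteristics, lists "Stage classification, duration of COPD, past treatment history, type of concomitant medications/therapies, history of cigarette smoking", among others.

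**Use.** Section 9 1)(3)[3] plans an "Explorative assessment of factors (patient demographic and baseline characteristics) that may affect the presence or absence of ADRs" and likewise "the presence or absence of ADRs set as the priority study item". Section 9 1)(4) draws on the same class of factors for FEV1, global efficacy and CAT. Under Section 9 2), for factors that may affect safety or efficacy, "the odds ratios and their 95% confidence intervals will be calculated, as appropriate", with forest plots as an option.

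**The concern.** A baseline factor should be fixed before the outcome can occur. Any use during a year of treatment is not: the outcome can itself trigger the exposure. Several priority items, such as cardiovascular events, urinary retention and pneumonia, are conditions for which a drug may be started. If that drug then enters the table as a factor, the association partly describes how the event was treated, not who was at risk of it. The same applies to efficacy when a COPD drug is added because a patient is getting worse: it would be associated with poor FEV1 or CAT for that reason alone.

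The ADR outcome is presence or absence over follow-up, so nothing in the planned comparison restores the time order. The final tabulations go into the re-examination report (Section 13), and risk factors shown in a forest plot may be read as guidance on which patients need care.

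**Working it through.** The protocol states no figure on this point, so there is none to reproduce. The check has two parts.

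**1. Can the listed items put the treatment and the event in order?**

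| Section 8 item | Timing information listed |
|---|---|
| 3) Prior COPD medication | 4 weeks before initiation, with category and product name |
| 4) Anoro Ellipta | start and end dates |
| 5) Concomitant medications | none; name and reason for use |
| 6) Non-drug COPD therapies | none; name only |
| 14) AEs | date of onset |

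An AE onset date exists, but no start date for the other treatment is listed to compare it with. The baseline entry for concomitant treatment cannot be loose wording for earlier treatment, because past treatment history is a separate entry in the same list and prior COPD medication is a separate study item ("Presence or absence of prior medication for COPD 4 weeks before the initiation of treatment").

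**2. How large could the distortion be?** Assume no causal effect. Let b be the share of all patients using a drug class for reasons unrelated to any ADR, and q the share of otherwise unexposed ADR patients in whom the class is started as treatment. Then

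- use among patients without an ADR = b
- use among patients with an ADR = p = b + (1 − b)q
- expected odds ratio = [p/(1 − p)] / [b/(1 − b)]

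Both b and q are assumptions. For b = 0.10, the denominator is 0.10/0.90 = 0.1111.

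| q | p | p/(1 − p) | Odds ratio |
|---|---|---|---|
| 0.10 | 0.19 | 0.2346 | 2.11 |
| 0.20 | 0.28 | 0.3889 | 3.50 |
| 0.30 | 0.37 | 0.5873 | 5.29 |

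Over b from 5% to 20% and q from 10% to 50%, the odds ratio runs from 1.56 (b = 0.20, q = 0.10: 0.3889/0.25) to 21.0 (b = 0.05, q = 0.50: p = 0.525, 1.1053/0.0526).

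For precision, take the target of 2000 patients and an assumed ADR incidence of 5%, giving 100 patients with an ADR and 1900 without. The Wald standard error of the log odds ratio is √[1/(100p) + 1/(100(1 − p)) + 1/(1900b) + 1/(1900(1 − b))]. With b = 0.10, the 95% intervals are 1.25 to 3.56, 2.21 to 5.55 and 3.43 to 8.15 for the three rows above. The mildest case (1.56) has an interval of 0.99 to 2.44, which just includes 1. ADR incidence changes the width of the interval, not the odds ratio.

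**Opposing effect.** If patients with an ADR stop early and so have less time to use any drug, their background use falls. Suppose it is 5% against 10% in the others, with q = 0. The odds ratio is then 0.0526/0.1111 = 0.47. With q = 0.10 added, p = 0.05 + 0.95 × 0.10 = 0.145 and the odds ratio is 0.1696/0.1111 = 1.53. The net bias depends on both mechanisms.

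If exposure is limited to use at initiation, neither mechanism operates, and the odds ratio under no effect is 1.

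**The case against.** **The heading says baseline, so baseline use is meant.** CAT, spirometry and exacerbation counts stand under the same heading and are also collected later, yet are naturally read there as baseline values. This answers only part of the point. CAT and spirometry have a scheduled measurement at initiation, and exacerbations are counted for the year before; concomitant treatment has no listed record at initiation to fall back on.

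**The data allow separation.** A reader might infer that earlier and later use cannot be told apart at all. The document does not support that. Item 3) names prior COPD drugs, so most add-on COPD drugs can be recognised. For other drugs, the reason for use in item 5) can be matched with pre-existing complications in item 2) and with AE diagnoses and onset dates in item 14). But the protocol states no such rule, a reason for use is not a start time, and item 6) lists neither. Section 8 is also not exhaustive, and the case report form (Attachment 4) is not shown; it may hold dates.

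**The analysis is exploratory, and details belong in the SAP.** Odds ratios are calculated as appropriate, and an SAP could redefine the factor. It could not recover a start time that was never collected, and the mismatch between collection window and label lies in the protocol itself.

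**The illustration is generous.** It needs one drug class to be started in 10% to 30% of ADR cases, while the ADR outcome pools many event types and the priority item alone spans eleven categories. That is fair: nothing in the protocol supports those shares, least of all for ADRs overall.

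**Conclusion.** The concern holds as a mismatch between what is collected and how it is classified. A variable recorded over the treatment period is listed as baseline and, through that label, becomes a candidate factor for ADRs and efficacy. Used as written, it can produce reverse-causal associations.

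The size is hypothetical: odds ratios of 2.1, 3.5 and 5.3 for assumed starting shares of 10%, 20% and 30% at an assumed 10% background use, before any opposing effect of shorter observation.

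Three stronger conclusions do not follow:

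- That the odds ratios will be reverse-causal in general. Treatment of the event affects only classes actually used to treat ADRs, and early stopping can pull the estimate the other way.
- That the same statement about odds ratios covers FEV1 and CAT. For scores, Section 9 2) describes means, quartiles and changes from baseline; the timing fault carries over, but these odds ratios do not.
- That labelling would rest on these estimates. Section 14 provides for considering amendments after an overall evaluation and does not tie them to the factor analysis.

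The point merits correction because it is cheap to remove, not because a wrong safety conclusion is shown to be likely.

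**What to change.** In Section 9 1)(2), define the factor as concomitant medication or non-drug COPD therapy already in use at initiation of Anoro Ellipta. Support it with a yes/no flag for use at initiation, or a start date, for Section 8 items 5) and 6), if the case report form does not already hold one. Take on-treatment concomitant use out of the baseline and factor lists and tabulate it descriptively.

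The cost is a wording change and one extra entry per medication or therapy at the sites. Because the new item is meant to change a safety and efficacy analysis, it may fall outside the minor changes exemplified in Section 15 1) and need an advance change notification to the agency.
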